**In our local public safety net hospital, one of the largest in the nation, significant proportions of patients who are referred by their primary care provider, and scheduled, for colonoscopy do not attend their appointments.** In 2014, colonoscopy no-show/cancellation rates were 41% in Hispanic patients, 58% in Caucasian patients, and 60% in African American patients. These numbers represent approximately 1150 people in one year in one health system who, despite being referred and scheduled for colonoscopy, were never screened for CRC because they did not complete this test. Evidence shows that safety net health systems are particularly impacted by this problem. We conducted interviews with 48 patients in our safety net hospital who were scheduled for colonoscopy - 100% of these patients reported that their provider had not offered any other CRC screening test option besides colonoscopy. In addition, when asked why they did not complete the test, many reported that their provider had never explained what a colonoscopy was or why it was needed. In addition, the majority of these patients had been scheduled for, but did not attend, prior colonoscopy appointments. Large numbers of patients are indicating they are unwilling to have a screening colonoscopy.

**B.1. Effective interventions that increase risk-based CRC screening for all patients have been developed but not compared nor combined. (RQ-1)** Providers have limited time to counsel patients about why CRC screening is important, which tests options are available, and what each test entails. Both patient navigation and tailored DVD interventions that can be delivered in the privacy of people's homes and are available when they are needed most have great potential to increase CRC screening and improve bowel preparation for those who choose colonoscopy. Such interventions supplement face-to-face clinical encounters, providing support and guidance for patients undergoing this unfamiliar, invasive procedure.

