**C.2. Design.** A three-group randomized controlled trial will be conducted to compare the effectiveness of two interventions to promote CRC screening test completion. Eligible men and women who were scheduled for colonoscopy in the endoscopy unit at Eskenazi Health (our safety net health system) but did not attend their appointment will be invited to participate. After baseline data are collected via structured telephone interviews, participants will be randomized to receive: 1) a mailed DVD titled *Time to ACT: Approaches to Colon Testing*; 2) the mailed DVD plus a patient navigator (PN) intervention; or 3) usual care (See Figure 2). (RQ-2, RQ-3, RQ-4, RQ-5)

Study Design and Schema

**C.3. Setting and Recruitment. (PC-2)** On a weekly basis, Eskenazi Health IT department will generate lists of age-eligible patients at average risk who did not attend their colonoscopy appointment. The list will include 2 groups of average risk patients who missed their appointment: 1) patients who had a colonoscopy screening ordered; and 2) patients who had a recent fecal immunochemical test (FIT) that was positive with a follow-up order for colonoscopy. Due to differences in physician ordering practices, the follow-up colonoscopy can be ordered as a colonoscopy screening, colonoscopy diagnostic, or colonoscopy high risk. Patients will be approved for contact by [name], Director of the Eskenazi Health Endoscopy Department. Patient information will be released to the study’s data manager, the Eskenazi Endoscopy Department’s Patient Navigator nurse, and trained research staff at the IU School of Nursing using secure electronic data transfer methods. Information disclosed is limited to that which is necessary to determine eligibility and to contact patients by mail and telephone. As a first step, the Endoscopy Patient Navigator nurse or nurse designee will screen patients by looking back 10 years and excluding any with a history of adenomatous polyps, sessile serrated polyps, or any mass suggestive of neoplasia. Patients with a history of hyperplastic polyps, lymphoid tissue, or no polyps will be

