recruited. To be eligible, these patients must: 1) have been referred for a colonoscopy that was not done (i.e, canceled or no show); and 2) be 50 to 75 years old if non-African American or 45-75 years old if African American. Patients meeting these inclusion criteria will be excluded for the following reasons: 1) unable to speak, read, and write English; 2) a personal history of having a colonoscopy at a non-Eskenazi Health location where polyps were found and they were the type that could turn into cancer; 3) FIT negative result in the past 12 months; 4) a personal history of CRC; 5) a personal history of conditions that place them at high risk for CRC such as ulcerative colitis, Crohn's disease, or known hereditary syndromes such as familial adenomatous polyposis or hereditary nonpolyposis colorectal cancer; 6) a family history of CRC which increases their risk; and 7) speech, hearing, cognitive, and/vision impairment. Trained research staff at the IU School of Nursing will recruit patients using procedures consistent with clinic and HIPAA requirements. Recruiters will send introductory letters, signed by the Principal Investigator and a co-investigator who is a member of the Eskenazi Medical Staff, along with a recruitment brochure and Study Information Sheet that explains the study to all approved patients. The letter informs patients that they will receive a phone call about the study within the next week unless they call a toll-free number to say they do not wish to be contacted. One week after letters are mailed, trained recruiters at the IU School of Nursing will call potentially eligible participants who have not opted-out to explain the study requirements, potential risks and compensation, and answer questions. Adequate speech, hearing, and cognition of potential participants will be confirmed by recruiters based upon the phone conversation. They will then proceed to determine eligibility, obtain both verbal informed consent and verbal HIPAA Authorization, and schedule a convenient time to conduct the baseline interview. Each participant who is not reached will be called back up to, but no more than, 10 times. Recruiters will record each call attempt including the date, time, disposition, and callback preference. Participants who decline to participate will be thanked for their time, with their response and reason for refusal recorded.

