**C.4. Intervention and Usual Care Descriptions. (PC-1, PC-2, PC-3, RQ-2, RQ-5).** The tailored DVD titled *"Time to ACT: Approaches to Colon Testing"* and patient navigator interventions are described in the following sections. All phases of intervention refinement will be conducted in consultation with our Community Advisory Board, which will be comprised of 8 members of the target population. Our Community Advisory Board (CAB), [name], our patient stakeholder and Chair of the CAB, and [name], Director of the Indiana University Simon Cancer Center's Office of Health Disparities and Community Engagement, will ensure the relevance of both interventions to a diverse group of users. By interacting with the patient navigator, participants will receive a barrier-reducing intervention that will be individualized based on their knowledge, health beliefs about CRC screening, and identified logistical barriers. The tailored DVD addresses these same theoretical concepts and will incorporate colors, screen designs, and music preferred by our CAB. Usual care in the Eskenazi Health System endoscopy department begins with referrals for screening

colonoscopy that are generated by primary care providers in this integrated health system. Primary care providers enter colonoscopy orders into the electronic health record which are immediately communicated to the endoscopy department. Endoscopy department staff schedule an appointment, typically within 4-5 weeks of the referral, and mail an information packet about the procedure along with written instructions for completing the bowel preparation. The packet includes instructions to call with any questions and if necessary, to reschedule the appointment. Within 1-2 days prior to the scheduled appointment, an endoscopy department nurse telephones each patient to remind him/her of their appointment and answer any questions about the procedure, including completing the bowel preparation.

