**C.12. Sample Size, Power Analyses (RQ-2, RQ-4, IR-3).** The revised sample size estimate of 115 per group for analyses is based on ensuring adequate power for Aim 1 (see Table 4). The main objective is to compare the 12-month CRC screening rates with any test among the three groups, so the binary outcome of any CRC screening test completion at 12 months as documented in the electronic medical record has driven calculation of our sample size. For Aim 1, we will first test whether there is any overall group difference in CRC screening completion rates using a chi-square test at 5% significance level. If a significant difference is observed, pairwise comparisons will be conducted at  $\alpha=1.7\%$  (5%/3 pairwise tests) to account for multiple testing. Expected CRC screening rates, based on prior studies demonstrating the effects of computer-tailored and PN interventions, are shown in Tables 1 and 2, respectively. We have revised our DVD only effect calculations from the original estimate of 15.5% to 20% for this group. We originally proposed a DVD only effect size of 15.5% based upon the average effect size of studies listed in Table 1. This 15.5% estimate assumed that the lowest rate observed in the DVD only group might be near 20% ([name], 2015) and lowered that rate even further to 15.5% to be more conservative, as statisticians typically assume very conservative effects when doing power calculations. However, by assuming a value closer to, but still less than the lowest rate observed in the literature for a comparable population (which was 22% seen in [name], 2015 per Table 1), the samples sizes can be reduced to 115 per group for Aim 1. This sample size will afford at least 80% power for all three comparisons per Table 4 below. To allow for an approximate 25% attrition which the project is experiencing as of May 31, 2019 and still have 115 per group for analyses, a total sample size of 450 enrolled subjects is required.

**Table 4. Revising the expected rate in the DVD group to 20% (still smaller than the smallest rate for a tailored intervention in Table 1)**

Comparison	Rates	Sample Size for Groups	Power
PN+DVD vs DVD only	44% vs 20%	115 vs 115	92%
PN+DVD vs Usual Care	44% vs 5%	115 vs 115	99%
DVD only vs Usual Care	20% vs 5%	115 vs 115	80%

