Several studies have shown that patient navigation is an effective method to increase CRC screening rates especially in minority groups with effect sizes shown in Table 2 (average of 33.7). We conservatively estimated a 44% (less than 33.7 + 20 = 54%) effect size for the PN + DVD since we will enroll patients who have previously canceled a screening colonoscopy appointment. For usual care, we used the estimate from [name], 2015 in Table 1 as it is most similar to the proposed study. See Table 5 below for summary. At 12 months, 115 in each group will yield at least 80% power for detecting the pair-wise differences (44% v. 20% v. 5%) in completion rates among the three groups using pair-wise chi-square tests or bivariate logistic regression models and a two-sided  $\alpha=.017$  level. Back-calculation, assuming an attrition rate that is approximately 25% from the sample size needed at 12 months, it requires that we approach 600 eligible subjects to enroll 450 (75% participation rate) and randomly assign them to the three intervention groups (150 per

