## E. Patient Population (RQ-2, RQ-3, RQ-4, PC-1, PC-2)

**E.1. Sample and eligibility criteria.** 450 people who canceled or did not attend their colonoscopy appointment will be enrolled in this study. Participants will be eligible if they are 50-75 years old if non-African American or 45-75 years old if African American and were referred to Eskenazi's endoscopy unit for a colonoscopy. Stratified block random assignment to each of three groups will be performed within 12 strata formed by crossing sex, three race/ethnicity groups, and two age levels (male/female, Black/White/Hispanic, age<65/age 65+) to ensure that the three randomized groups are comparable in distribution of sex, race/ethnicity, and age. At the completion of the baseline interview, patients will be randomly assigned to the tailored DVD-only group, the tailored DVD plus patient navigator group, or usual care. Based on the 65% participation rate we achieved in our recent R01 conducted in this same health system, we conservatively estimated our participation rate at 55%. However, our actual, cumulative participation rate for eligible subjects was 75% through May 31, 2019. Therefore, we will need to contact approximately 600 eligible people to enroll 450. Data from 2014

indicate the availability of 1150 potentially eligible patients during that 12 month period (See Table 6). An estimated 2200 would be available over the 24 month enrollment period. Based on our preliminary studies, no more than 20% attrition was anticipated at 9 months. Actual data from Year 3 of this project as of May 31, 2019 shows an attrition rate closer to 25% at the 6 month follow-up timepoint. This approximate 25% rate is being used in re-calculating the sample size required.

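### Patients who canceled but already hold a new colonoscopy date can be enrolled and are not identified anywhere, which could dilute the DVD versus usual care contrast

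*Combined protocol and SAP*

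**What the plan says.** **Who is eligible.** The inclusion criterion in C.3, repeated in section B of Protection of Human Subjects, is that patients "have been referred for a colonoscopy that was not done (i.e, canceled or no show" and are in the age range. E.1 gives the sample as "450 people who canceled or did not attend their colonoscopy appointment will be enrolled in this study". The weekly source list in C.3 is described more narrowly: the IT department will "generate lists of age-eligible patients at average risk who did not attend their colonoscopy appointment".

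**Rescheduling is routine.** On the information packet sent under usual care, C.4 says: "The packet includes instructions to call with any questions and if necessary, to reschedule the appointment". E.2 describes the same arrangement.

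**What is checked.** The nurse's look-back in C.3 covers polyps and masses. The seven exclusions cover language, polyp and CRC history, a recent negative FIT, high-risk conditions, family history and impairments. A check that a colonoscopy is still needed appears only for re-contacted patients with earlier polyps, and a rebooked patient would pass it. Randomization (E.1) is stratified by sex, race/ethnicity and age. C.13 names no covariate for appointment status.

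**How the trial is sized.** C.12 assumes 44%, 20% and 5% completion at 12 months for PN+DVD, DVD only and usual care, with 115 per arm. The 5% comes from a prior trial in Table 1. The PN+DVD rate was set conservatively "since we will enroll patients who have previously canceled a screening colonoscopy appointment". Section B says that the roughly 1150 patients who did not attend in 2014 "were never screened for CRC because they did not complete this test".

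**The concern.** A patient who phones to move an appointment has canceled one colonoscopy and holds a date for another. As written, the criterion admits that patient. First appointments typically fall 4-5 weeks after referral (C.4). Recruitment then takes a letter, a week's wait, up to 10 call-backs and a scheduled baseline interview, and the first navigator call comes about two weeks after the DVD is mailed. If rebooking takes about as long as a first booking, which the documents do not say, the new colonoscopy could happen around or before intervention delivery and still count as a 12-month success.

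Two things are at stake. Completions that occur regardless of arm push usual care above the assumed 5% and narrow the differences on which the trial is sized. The result would also describe a mixture of patients who would otherwise go unscreened and patients already in the queue, with no recorded variable to separate them.

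**Working it through.** **Inputs.** Rates 44%, 20% and 5%, and 115 per arm (C.12, Table 4). Pairwise alpha .017 ("5%/3 pairwise tests) to account for multiple testing"), two-sided ("using pair-wise chi-square tests or bivariate logistic regression models and a two-sided" level). 150 randomized per arm (C.12). Primary outcome taken from records for all participants, including dropouts (C.13). Two quantities are assumed: the rebooked share *f*, and the rebooked completion rate *r*. For *r* the only system-level figure is 811/1962 = 41.3% of ordered colonoscopies (Table 6).

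**Step 1: reproduce Table 4.** Power = Φ{[d − 1/n − z·√(2p̄(1−p̄)/n)] / √[(p₁(1−p₁)+p₂(1−p₂))/n]}, with z = 2.387. For DVD versus usual care, d = 0.15, p̄ = 0.125, n = 115:

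(0.15 − 0.0087 − 2.387×0.0436)/0.0425 = 0.876, so power is 81%.

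The plan states 80%. The same formula gives 92% for PN+DVD versus DVD (stated 92%) and over 99% for PN+DVD versus usual care (stated 99%). Without the continuity correction, DVD versus usual care is 86%. The corrected formula needs 113 per arm for 80% power, so 115 leaves almost no slack on this contrast.

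**Step 2: dilute the rates.** Arm rate = (1−f)·p + f·r, with *r* equal in all arms, meaning booked patients do not respond to either intervention. Example at f = 10%: usual care 0.9×5 + 0.1×41.3 = 8.6%; DVD 0.9×20 + 4.13 = 22.1%; PN+DVD 0.9×44 + 4.13 = 43.7%. The DVD difference drops from 15 to 13.5 points, and at n = 115 power is Φ[(0.135 − 0.0087 − 2.387×0.0476)/0.0467] = 61%.

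**Step 3: range at r = 41.3%, continuity-corrected.**

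| f | Usual care | DVD | PN+DVD | DVD vs UC, n=115 | DVD vs UC, n=150 | PN+DVD vs DVD, n=115 | PN+DVD vs DVD, n=150 |
|---|---|---|---|---|---|---|---|
| 0 | 5.0% | 20.0% | 44.0% | 81% | 92% | 92% | 98% |
| 5% | 6.8% | 21.1% | 43.9% | 71% | 85% | 89% | 96% |
| 10% | 8.6% | 22.1% | 43.7% | 61% | 76% | 84% | 94% |
| 20% | 12.3% | 24.3% | 43.5% | 42% | 56% | 71% | 85% |

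PN+DVD versus usual care stays above 99% throughout this table.

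**Step 4: vary the completion rate.** At f = 10% and n = 115, DVD versus usual care is 67% if r = 20%, 56% if r = 60% and 52% if r = 80%.

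**Step 5: let booked patients respond fully.** Suppose they gain the planned 15 points from the DVD (41.3% to 56.3%) and a further 24 from navigation. The DVD difference is then still 15 points, but on a higher base rate with more variance. DVD versus usual care is 70% at f = 10% and 62% at f = 20% with 115 per arm, or 84% and 77% with 150. PN+DVD versus DVD with 150 per arm is 96-97%.

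**The case against.** The strongest reply is that the text is silent rather than permissive. The weekly list is of patients who did not attend, and nothing says that someone who phones to move a date is coded as canceled or stays on the list. That is fair as regards how many such patients there are. It does not close the gap, because the eligibility criterion and E.1 both count cancellation as qualifying.

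Second, both drivers of the size are assumed. The share has no source, and 41.3% is completion among all orders, not among people who have already canceled once. Section B reports that most interviewed patients had missed earlier appointments too. This stands, so the figures are scenarios.

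Third, booked patients are not inert. C.1 describes navigation as serving people scheduled for colonoscopy, and navigators call those with an appointment 1-2 days beforehand (C.4.b). This also stands: zero response is the pessimistic end, and Step 5 shows the smaller loss.

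Fourth, records supply the outcome for about 150 per arm. That cushions the loss but does not remove it.

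A reader might go further and infer that rebooked patients raise screening in every arm. Under the plan's own rates PN+DVD rises only if they complete at more than 44%; at 41.3% it dips slightly. A reader might also infer bias between arms. Randomization balances booked status on average, so the documents do not support that. Nor do they support the inference that the trial is underpowered overall, since serious loss is largely confined to DVD versus usual care.

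Baseline readiness and screening-experience items, and the individual characteristics in the primary model (C.13), may pick up some of this. None is said to record a pending appointment.

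**Conclusion.** The gap is real: patients already holding a new date are eligible as the criterion is written, and the plan has no variable that identifies them. The consequence is dilution, loss of precision and a less clear target population. Its size rests on a rebooked share that the documents do not give. For a share of 5-20%, completion near 41% and no response to the interventions, DVD versus usual care loses about 10 to 39 points of power at 115 per arm (81% to 71-42%) and about 7 to 36 points at 150 (92% to 85-56%). With full response at a 10-20% share, the loss is about 11 to 19 points at 115 and 8 to 15 at 150. If very few participants were rebooked, the effect is negligible. This is a worthwhile, inexpensive improvement and not a flaw that invalidates the comparison.

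**What to change.** 1. For every participant, extract from the scheduling record whether a colonoscopy was already booked on the baseline/randomization date. It must reflect status on that date, not later bookings, so that it is a true baseline variable.
2. Prespecify the flag as a covariate in the primary logistic model, whether or not it meets the p < .20 imbalance rule in C.13.
3. Repeat the primary analysis excluding flagged participants, and report the flagged share by arm.
4. For any remaining accrual, state whether a pending date affects eligibility.

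**Gain.** In a simulation at 115 per arm with 10% rebooked and no response, stratifying on the flag raised power for DVD versus usual care from about 68% to 72% when booked patients complete at 41%, and from about 58% to 76% when they complete at 80% (no continuity correction).

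**Cost.** One extra extracted field and one extra analysis. The exclusion analysis is smaller (with 10% flagged, 115 × 0.9 ≈ 103 per arm) and should be labeled as a sensitivity analysis. Excluding such patients at entry instead would change the target population late in accrual, so it is a trade-off and not needed for this repair.

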**Aim 2. Examine age, race/ethnicity, sex and income as potential moderators of intervention effects. (RQ-4, HT-1, HT-2, HT-3, HT-4)** We will fit multivariable models as in Aim 1, except now including interaction terms for age (< 65, age 65+), race/ethnicity (Non-hispanic Black, Non-hispanic White), sex (male, female), and annual income (<\$15,000, ≥\$15,000), respectively. Moderators will be identified by significant interaction terms in regression models. The key moderation effects of interest will be between PN+DVD vs. DVD only. Moderation of PN+DVD vs. usual care, and DVD only vs. usual care also will be examined. Hispanics will be excluded from race/ethnicity interaction tests due to small sample sizes.

**Aim 3. Examine changes in knowledge and health beliefs (knowledge, perceived risk, perceived benefits, barriers, and self-efficacy) as potential mediators of intervention effects. (RQ-6)** Mediation analysis will be conducted to identify potential mediators. Specifically, for each of the variables (changes in knowledge, perceived risk, perceived benefits, perceived barriers, and self-efficacy) mediation effects will be estimated in an logistic regression setting, fitting the appropriate mediation models using MPlus and then testing indirect effects using the percentile bootstrap approach to estimate the indirect effect. We will fit models that estimate the effects of PN plus DVD vs usual care and DVD only vs usual care, and also models that compare the strength of the indirect effects between the PN plus DVD and DVD only arms. We expect to see a difference in mediation effects mainly on barriers, with the PN plus DVD having a greater mediation effect on barriers than DVD only.

**C.14. Potential problems, strategies and benchmarks for success.** Potential problems are described below along with plans to minimize them. (*IR-6, MD-1, MD-2, MD-4*)

- *Loss to follow-up:* It is anticipated that there will be some loss to follow-up because of participant dropout, death, or relocation. Based attrition data through May 31,2019 , we estimate the loss to be approximately 25% over the 9-month study period, which has been accounted for in the revised power analysis and sample size determination.
- *Limited internal validity:* Randomization will minimize the influence of extraneous variables on outcomes.

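### Eligibility starts at 45 for African American patients and at 50 for others, so the Aim 2 Black-versus-White interaction compares unequal age ranges; an age 50-75 analysis should be prespecified

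*Combined protocol and SAP*

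**What the plan says.** C.3 (Setting and Recruitment) admits patients who "be 50 to 75 years old if non-African American or 45-75 years old if African American". E.1 repeats the rule ("Participants will be eligible if they are 50-75 years old if non-African American or 45-75 years old if African American"), as does the recruitment text under Protection of Human Subjects.

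For Aim 2, C.13 refits the Aim 1 models "including interaction terms for age (< 65, age 65+), race/ethnicity (Non-hispanic Black, Non-hispanic White), sex (male, female") and income below or at least $15,000. The wording reads as one moderator at a time. The decision rule is "Moderators will be identified by significant interaction terms in regression models", and "The key moderation effects of interest will be between PN+DVD vs. DVD only". The race test leaves out one group: "Hispanics will be excluded from race/ethnicity interaction tests due to small sample sizes".

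The randomization strata in E.1 use the same age cut at 65, crossed with sex and race/ethnicity. C.12 calls Aim 2 exploratory and claims no power for it. C.13 allows sensitivity analyses as needed for all aims but names none for this comparison.

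**The concern.** Race and the 45-49 age band are tied together by the eligibility rule. No White participant can be under 50, so the data cannot separate being Black from being under 50 within that band. The only age term in Aim 2 puts 45-49 in the same class as 50-64.

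Nothing else in the plan closes the gap. The C.13 covariate rule looks for baseline differences between randomized groups at p < .20, so it is not designed to find an age difference between races. Even if age were added as a main effect, that would not remove confounding of an arm-by-race interaction. That needs either an arm-by-age term fine enough to separate 45-49 or a common age range.

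At stake is the use to be made of Aim 2. C.12 hopes to identify subgroups who may not need the more intensive support of a navigator. A Black-White difference that partly reflects the youngest band would then carry the wrong label. The affected group is the larger one: 749 of the 1151 non-completers in Table 6 (65%) are Black.

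**Working it through.** **Inputs from the plan.** Screening rates are 44% for PN+DVD and 20% for DVD only, with 115 analysed per arm (C.12, Table 4). Colonoscopy orders were 64% Black and 34% White (Table 6). This gives 115 × 0.64 = 73.6, about 74 Black participants per arm, and 115 × 0.34 = 39.1, about 39 White.

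**Assumptions, not in the documents.** A share s = 10-30% of Black participants is aged 45-49. The PN+DVD effect differs by 10-20 percentage points below 50. There is no true race difference at any given age. The DVD-only rate is 20% throughout.

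**Step 1: check of the planning rates.** The plan gives no figure for the race test, so only Table 4 can be reproduced. A continuity-corrected chi-square at two-sided 0.017 for 44% vs 20% gives z = (0.24 − 1/115 − 2.387 × √(2 × 0.32 × 0.68/115)) / √((0.44 × 0.56 + 0.20 × 0.80)/115) = 1.42. Power is 92.2%, against 92% stated. The other two rows come out at >99.9% (99% stated) and 81.0% (80% stated).

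**Step 2: spurious interaction.** The PN+DVD rate among Black participants is b = (1 − s) × 0.44 + s × x, where x is the rate at 45-49. White participants stay at 44%. The DVD-only odds cancel, so the spurious Black:White ratio of odds ratios (ROR) is [b/(1 − b)] / [0.44/0.56].

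| s | x | b | ROR | chance of p < .05 |
|---|---|---|---|---|
| 10% | 0.34 | 0.43 | 0.96 | 5.1% |
| 10% | 0.54 | 0.45 | 1.04 | 5.1% |
| 10% | 0.24 | 0.42 | 0.92 | 5.2% |
| 10% | 0.64 | 0.46 | 1.08 | 5.2% |
| 30% | 0.34 | 0.41 | 0.88 | 5.4% |
| 30% | 0.54 | 0.47 | 1.13 | 5.4% |
| 30% | 0.24 | 0.38 | 0.78 | 6.8% |
| 30% | 0.64 | 0.50 | 1.27 | 6.7% |

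The last column is Φ(z − 1.96) + Φ(−z − 1.96), with z = log(ROR)/SE. As an outer bound, if the effect vanishes at 45-49 (x = 0.20) and s = 30%, the ROR is 0.74 and the rejection rate 7.6%.

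**Step 3: precision of the race test.** SE of log ROR = √[(1/74 + 1/39) × (1/(0.44 × 0.56) + 1/(0.20 × 0.80))] = √(0.03916 × 10.308) = 0.635. A 95% interval runs from the estimate divided by exp(1.96 × 0.635) = 3.5 to the estimate times 3.5. For 80% power at the 5% level the true ROR would have to be exp(2.80 × 0.635), about 5.9.

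C.13 takes the primary outcome from medical records for all participants, so the analysed number may be nearer 150 per arm (96 Black, 51 White). The SE is then 0.56. The largest rejection rate in the table becomes 7.3%, and the outer bound 8.4%.

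**Step 4: age affecting the screening rate only.** Suppose the odds of screening at 45-49 are halved or doubled in both arms and the intervention odds ratio stays at 3.14. For s between 5% and 30%, the spurious ROR is 0.97-1.00 and rejection stays at 5.0%.

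**Step 5: restriction to ages 50-75.** The spurious ROR returns to 1.00 in these scenarios. With 74 × (1 − s) Black participants per arm, the SE is 0.647 at s = 10% and 0.681 at s = 30%. Against 0.635, these are increases of 2% and 7%.

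**The case against.** The strongest case on the other side is that this hardly matters. The spurious ratio lies far inside an interval that spans a factor of 3.5 either way, and the decision rule barely moves. The upper assumptions are also generous. If ages were spread evenly, 45-49 would be 5 of 31 eligible years, about 16%, and a 20-point change means that a 24-point effect almost disappears or nearly doubles below 50. Nothing in the documents suggests that. All of this stands and keeps the point minor.

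It can also be said that Aim 2 is descriptive. Black patients as actually eligible, aged 45-75, are a legitimate group to report, and restriction to 50-75 does not equalize age within that range, or income. This stands too. It argues against making the restricted analysis the only race test, but not against adding it.

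Some stronger readings are not supported. A reader might infer that any age effect on screening would surface as race moderation; step 4 shows that it would not. A reader might also point to the guideline starting age of 50 in the Background and Significance sections as a reason to expect a different response below 50. That text is background to the application. The DVD content described in C.4.a states no starting age, and every participant had already been referred for colonoscopy.

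**Conclusion.** The point holds as a minor gap. The eligibility rule builds an age difference into the Black-White contrast, and the plan has no step that removes it. The result is biased as a statement about race only if the intervention effect itself differs below 50. Under the assumed 10-30% share and 10-20 point difference, the spurious ROR reaches at most 0.92 or 1.08 at the low share and 0.78 or 1.27 at the high share, with a false-positive rate of about 7% at most. The share and the difference in effect are both assumptions.

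A reader might conclude that the plan is likely to produce a false race finding, or that the trial's main result is at risk. Neither follows. Aim 2 is exploratory, randomization is stratified by race so the arm comparisons within each race remain randomized, and Aim 1 does not depend on this contrast. What is exposed is the label put on a Black-White difference.

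**What to change.** Add to C.13, Aim 2, before outcome data are examined: the arm-by-race interaction will also be estimated in participants aged 50-75, the range open to both races, and a race moderator will be claimed only if the estimate is consistent in that analysis. The team should write down what it will count as consistent, for example the same direction and a similar size.

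The analysis in all eligible Black and White participants stays as planned, all participants stay in Aim 1, and eligibility is unchanged. Age is already collected at baseline. The cost is one extra analysis, with a standard error about 2% larger if 10% of Black participants are 45-49 and about 7% larger if 30% are.
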